### 5.3 Main lumpectomy specimen and shaved cavity margins nomenclature

Throughout this protocol, reference is made to the orientation of the main specimen, the SCMs and the lumpectomy cavity walls. When a lumpectomy is performed, there are typically 6 surfaces defined for orienting the main specimen. Typically, final margin assessment is made for each orientation. **Figure 4** shows a schematic representation of the nomenclature for the lumpectomy cavity margins for a right-sided breast lumpectomy, showing 5 orientations. The sixth orientation (not shown in the figure) is the “anterior” margin which is the margin nearest to the skin. For surgeons performing selective or comprehensive SCMs, a shave may not be removed from the

LUMICELL CONFIDENTIAL

This document is confidential. Do not disclose or use except as authorized.

anterior orientation if the lumpectomy cavity extends to the skin or subcutaneous fat. Similarly, a SCM from the posterior orientation (also referred to as “deep”) may not be removed if the lumpectomy cavity reaches the fascia over the pectoralis major or serratus anterior muscle. Shaved cavity margins removed under the guidance of the LUM Imaging System will be named “therapeutic shaves” to distinguish them from standard of care SCM. Please see Appendix C for the guidelines on naming the resected tissue.

**Figure 4:** Schematic representation of the surfaces of the lumpectomy cavity walls (white circle). The posterior margin is nearest the fascia of the pectoral muscle. The anterior margin (not shown) is nearest the skin.

#### 5.4 Phase C study description

Data collected during this study will be used to further refine and verify the tumor detection algorithm.

Phase C will consist of up to 5 patients per surgeon, with 1-3 surgeons per site and up to 20 sites. The maximum number of patients participating in the study is 250. The assessment for completing the training will be done in collaboration between Luminell and each surgeon and will be documented. Surgeons may enroll more than 5 subjects if needed to complete training, or if more subjects are needed to complete the tumor detection algorithm verification.

Subjects undergoing a lumpectomy procedure to treat primary breast cancer will be injected with LUM015  $4 \pm 2$  hours prior to surgery at a dose of 1.0 mg/kg. The sequence of events during the surgical procedure will vary based on the standard of care used by the surgeon (Table 1).

Patients will receive the standard of care practices for each site, including any standard of care shaves. Then, the Luminell System is used and Luminell positive tissue should be removed. Please see Appendix B for more details on handling, inking and naming the resected tissue.

In addition, selected institutions will participate in a sub-study as described in Appendix D.

##### 5.4.1 SOC and study procedure

The surgeon will attempt to remove the main specimen with grossly negative margins. The surgeon may remove additional tissue based on intraoperative examination of the main specimen by methods including, but not limited to, palpation (of the main specimen or cavity walls), X-ray imaging, or visual examination. Some surgeons may proceed with comprehensive or selective shaves as part of their standard of care procedure. After any SOC shaves are obtained, the surgeon will conduct the cavity initialization step per protocol and then use the LUM Imaging System to

LUMICELL CONFIDENTIAL

This document is confidential. Do not disclose or use except as authorized.

scan the lumpectomy cavity walls, save images from all the cavity orientations and remove therapeutic cavity shaves as indicated by the Luminicell display. The main specimen, the additional tissue and all SCMs will be handled and named as described in Appendix B and C.

#### 5.4.2 Recording surgeon's decisions

[figure not shown]
During the LUM imaging procedure, if the surgeon decides to take a different action than the one suggested by the LUM Imaging System, the reason must be documented. The surgeon must notify the computer operator or clinical coordinator at that moment and they will note the reason in the study worksheets. This information will then be transferred to the case report forms. This is of utmost importance for evaluating the impact of the LUM Imaging System in guiding removal of tissue to obtain negative margins. If a shave is not taken when indicated by the Luminicell system, a protocol deviation will be recorded.

#### 5.4.3 Final margin assessment

Final margin assessment for a given orientation is done on the outermost surface resected for that specific orientation (see **Figure 5**). This surface could be on the main specimen, the SOC shaves or the therapeutic shaves. All the resected tissue will be handled and processed for margin assessment following the institution's current practices for breast conserving surgeries.

LUMICELL CONFIDENTIAL

This document is confidential. Do not disclose or use except as authorized.

**Figure 5:** Final margin assessment for a given orientation is based on the outermost surface resected (marked in red in the sketch). For the example in the sketch, final margin assessment for the medial orientation is based on pathology of the main specimen. Final margin assessments for the lateral orientation is based on the therapeutic shave. Final margin assessment for the superior orientation is based on the selective or comprehensive shave. Final margin assessment for the inferior orientation should be based on the therapeutic shave.

#### 5.4.4 Safety observations

All subjects will be observed to assess the safety of LUM015 with standard preoperative, intraoperative and postoperative monitoring from the time of injection to the time they are discharged from the hospital. The subject will have a final safety assessment at the first post-operative visit. All subjects will continue their enrollment and be followed in the study until their medical team determines that no further surgical intervention is required. Further details on follow up are included in section 8.5.

#### 5.4.5 Other general procedures and injection of LUM015

For subjects with non-palpable tumors, an ultrasound, mammogram or MRI-guided localization procedure may be performed prior to or the same day as the surgery. Also, patients having a sentinel lymph node (SLN) mapping procedure may be injected with the radio-tracer Technetium-99 (Tc-99) per standard of care. LUM015 may be injected before or after any of these procedures, as long as it is injected  $4 \pm 2$  hours prior to surgery.

Prior to the surgery, the LUM Imaging Device of the size selected by the surgeon will be positioned in the operating room and an initialization procedure will be conducted to ensure that the performance parameters of the device are within defined specifications. If during the initialization

LUMICELL CONFIDENTIAL

This document is confidential. Do not disclose or use except as authorized.

procedures, the performance parameters are outside the defined specification, the user is prompted to discontinue use of the device. If the error cannot be fixed within a reasonable time in the operating room, these patients will receive standard of care treatment and will not be imaged with the LUM Imaging Device. These patients will be followed and monitored for safety the same way as those patients that undergo imaging with the LUM Imaging Device. The patients that are not imaged with the LUM Imaging Device will be included in the safety cohort but will not be part of the efficacy cohorts and will not be included in the total number of patients for training purposes. To avoid excessive tissue resection based on LUM015 signal during this investigational study, surgeons will take no more than 2 therapeutic shaves in a given orientation.

#### 5.4.6 Sentinel lymph node mapping procedures

Dyes used for SLN mapping have fluorescence absorption and emission spectra that overlaps with those from Cy5 (dye conjugated to LUM015). When dyes are used for SLN mapping, they are injected intra-tumoral or peri-tumoral soon after the patient is put under anesthesia and prior to the lumpectomy procedure. Therefore, subjects having injection of dyes for SLN mapping prior to completing the Lumicell imaging procedure are excluded from this study. Recognize that injection of dyes for SLN mapping may occur after completing the Lumicell imaging procedure, but not prior to the imaging procedure.

Patients having SLN mapping procedures may be injected with the radio-tracer Tc-99. In the event that not enough signal is produced from Tc-99, the surgeon may elect to inject a dye to assist in the mapping procedure. If this occurs, these subjects will be excluded from the efficacy cohort but will remain in the safety analysis cohort. The surgeon, at their own discretion, may elect to image the lumpectomy cavity with the LUM System; however, that data will be used as reference only. These subjects will not count towards the total number of patients required to complete the training for that surgeon.

#### 5.4.7 Exploratory study: imaging of sentinel lymph nodes with the LUM Imaging System

[figure not shown]
In order to explore whether the LUM Imaging System can be used to detect sentinel lymph nodes with or without metastatic cancer, this protocol pursues an exploratory endpoint of collecting images of sentinel lymph nodes. At the surgeon's discretion, once the sentinel lymph nodes are identified with the radio-tracer, the surgeon can use the LUM Imaging System to image the sentinel lymph nodes *in vivo*. Regardless of whether the sentinel lymph nodes are imaged *in vivo*, the surgeon will have the option to image the resected sentinel lymph nodes with the LUM Imaging System in the operating room. Imaging data will be compared against pathology assessment of the resected nodes on whether these contain cancer or not.

LUMICELL CONFIDENTIAL

This document is confidential. Do not disclose or use except as authorized.

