## 4.3 LUM015 imaging agent

Lumicell engineered LUM015, a fluorescence-based imaging agent that accumulates within and around cells. In regions enriched with cathepsin enzymes, such as cancer cells, LUM015 is altered to produce a fluorescent signal. In its nominal state, the fluorescence of LUM015 is suppressed by an internal quencher molecule (QSY21). The presence of cathepsin enzymes is not fully confined to cancer cells; hence, data from this study will help determine the cancer localization properties of LUM015. Once cathepsin enzymes cleave LUM015 at its amino acid backbone, the quencher is released and the fluorescent dye (Cy5) in LUM015 emits detectable fluorescence (**Figure 1**). The absorption and emission wavelength maxima for Cy5 are 649 nm and 670 nm respectively. LUM015 employs a fluorescent molecule with excitation and emission in the far red spectrum (< 700 nm wavelength) because in that range light can travel effectively through 1mm of tissue and tissue autofluorescence is minimal, allowing higher sensitivity due to lower background [11].

**Figure 1:** Schematic representation of LUM015.

Cathepsins are a family of enzymes that are involved in the degradation of the extracellular matrix to allow tumor growth and progression. These enzymes are upregulated in most human cancers and are also present in tumor associated macrophages at the tumor's invasive front [12-16]. Platt et. al. showed 60-fold higher cathepsin activity in breast cancer tissue than in healthy breast tissue [17]. Others report over-expression of cathepsin enzymes (B, K, L and D) in ductal carcinoma *in situ* as well as in invasive carcinomas (lobular and ductal) [13, 17-20]. Also, cathepsin B is typically over-expressed in inflammatory breast cancer, one of the most lethal forms of primary breast cancer. [21, 22]. The peptide sequence used in LUM015 is a pan-cathepsin substrate meaning that it will be cleaved by multiple enzymes of the cathepsin family. Because high activity of cathepsin enzymes is found in tumor cells and tumor associated macrophages surrounding the tumor at the invasive front, these enzymes provide an excellent marker for activating LUM015 at the tumor margin. The fluorescence of LUM015 is then detected with the LUM Imaging System

LUMICELL CONFIDENTIAL

[figure not shown]
This document is confidential. Do not disclose or use except as authorized.

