## 6.2 Exclusion criteria

*Subjects who exhibit any of the following conditions at screening will not be eligible for admission into the study.*

- 6.2.1 Subjects who are treated for bilateral breast cancer resection procedure.
- 6.2.2 Subjects who are pregnant at the time of diagnosis of their breast cancer; this exclusion is necessary because the teratogenic properties of LUM015 are unknown. Because there is an unknown but potential risk of adverse events in nursing infants secondary to treatment of the mother with LUM015, breastfeeding should be discontinued if the mother is treated with LUM015.
- 6.2.3 Subjects who are sexually active and not willing/able to use medically acceptable forms of contraception (hormonal or barrier method of birth control, abstinence) upon entering the study and for 60 days after injection of LUM015. Should a woman become pregnant or suspect she is pregnant while participating in this study, she should inform her treating physician immediately. Breast cancer patients are routinely advised against becoming pregnant during treatment, so this requirement does not differ from standard of care.
- 6.2.4 Subjects who have taken an investigational drug within 30 days of enrollment.

LUMICELL CONFIDENTIAL

This document is confidential. Do not disclose or use except as authorized.

- 6.2.5 Subjects with prolonged QTc interval defined as greater than 480 ms.
- 6.2.6 Subjects who will have administration of methylene blue or any dye for sentinel lymph node mapping on the day of the surgery prior to imaging the lumpectomy cavity with the LUM Imaging Device.
- 6.2.7 Subjects who have not recovered from adverse events due to other pharmaceutical or diagnostic agents.
- 6.2.8 Subjects with uncontrolled hypertension defined as persistent systolic blood pressure > 180 mm Hg, or diastolic blood pressure > 110 mm Hg; those subjects with known HTN should be stable within these ranges while under pharmaceutical therapy.
- 6.2.9 History of allergic reaction to polyethylene glycol (PEG).
- 6.2.10 History of allergic reaction to any oral or intravenous contrast agents.
- 6.2.11 Uncontrolled intercurrent illness including, but not limited to ongoing or active infection, symptomatic congestive heart failure, unstable angina pectoris, cardiac arrhythmia, COPD or asthma requiring hospitalization within the past 12 months, or psychiatric illness/social situations that would limit compliance with study requirements.

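### Sentinel nodes may be imaged after a mapping dye that overlaps Cy5, and the exploratory node-versus-pathology comparison has no dye condition and no record of dye exposure

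*Protocol*

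**What the plan says.** Three parts of the protocol bear on this.

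- **The optical problem (5.4.6).** The protocol states as fact: "Dyes used for SLN mapping have fluorescence absorption and emission spectra that overlaps with those from Cy5 (dye conjugated to LUM015". Section 4.3 locates the fluorophore: "The absorption and emission wavelength maxima for Cy5 are 649 nm and 670 nm respectively".
- **The dye rule (5.4.6 and 6.2.6).** Because of the overlap, subjects who receive a mapping dye before LUM imaging are excluded. Dye at a later point is allowed: "injection of dyes for SLN mapping may occur after completing the Lumicell imaging procedure, but not prior to the imaging procedure". The matching exclusion criterion, 6.2.6, covers dye given on the day of surgery "prior to imaging the lumpectomy cavity with the LUM Imaging Device". Separately, 5.4.6 lets the surgeon add a dye if the Tc-99 signal is too weak. Those subjects leave the efficacy cohort and stay in the safety cohort, and any cavity images from them serve only as reference.
- **The node study (5.4.7).** In vivo node imaging is at the surgeon's discretion after the nodes have been located with the radio-tracer. Whether or not that was done, "the surgeon will have the option to image the resected sentinel lymph nodes with the LUM Imaging System in the operating room". The analysis is a single sentence: "Imaging data will be compared against pathology assessment of the resected nodes on whether these contain cancer or not".

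**The concern.** The protocol recognises that a mapping dye can interfere with the LUM signal and applies that reasoning to the cavity. It does not apply it to the nodes. Yet sentinel nodes are the tissue that a mapping dye is meant to reach, and the rule protecting the cavity works by moving dye to a later time, which is when nodes are removed and imaged.

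The exploratory question is whether the system can detect sentinel nodes with or without metastatic cancer. If some of the compared images come from dye-exposed nodes, the signal in those images cannot be attributed to LUM015 alone. If dye exposure is not recorded against each image, the affected nodes may not be identifiable afterwards, so the problem might not be repairable at analysis.

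**Working it through.** No arithmetic applies. The plan gives no sample size, rate or threshold for the node comparison, so there is no figure to reproduce. The check is whether a sequence that complies with every rule can put a dye-exposed node into the comparison, and whether any other rule takes it out.

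**Step 1: a compliant sequence.**

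1. The cavity is imaged with no dye given. This satisfies 5.4.6 and 6.2.6.
2. A mapping dye is then injected. Section 5.4.6 allows this.
3. The sentinel node is resected and imaged in the operating room. Section 5.4.7 allows this.
4. The image is compared with pathology, as 5.4.7 provides.

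No step breaches the protocol. Moreover, any dye used to find a node is given before that node is removed, so an ex vivo image of that node is necessarily taken after the dye.

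**Step 2: rules that might remove the node.**

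| Place | What it does | Does it remove a post-dye node image? |
|---|---|---|
| Protocol 6.2.6 | Excludes dye before cavity imaging | No; it ends at cavity imaging |
| Protocol 5.4.6, rescue dye | Removes the subject from the efficacy cohort; cavity images become reference only | Not stated; node images are not mentioned |
| Protocol 5.4.7 | In vivo imaging follows location by radio-tracer | No; a tracer-located node may also hold dye |
| Protocol 15.3 | Includes imaged subjects by default unless specified otherwise | No; nothing is specified for nodes |
| SAP section 2 | Defines mITT as all imaged patients | No; no dye rule |
| SAP 4.8.3 | Lists labels under which images are dropped (such as retaken images and lens issues) | No; there is no dye label |
| SAP 3.6 and 4.9 | Limit exploratory work to tissue types in therapeutic shaves | No; there is no node analysis |

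**Step 3: can the instrument sort it out?** Protocol 4.5 describes software that compares image intensity with a threshold set from initial cavity images. The documents describe no means of separating two overlapping fluorophores.

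**Step 4: size and direction.** The only relevant input is the statement of overlap, which covers both absorption and emission. Overlapping emission could add signal; overlapping absorption could reduce true signal. The documents give no relative brightness, no device response to any dye, and no share of nodes exposed. Neither the size nor the direction of the error follows.

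**The case against.** **Much of this is already handled.** The usual use of a mapping dye, soon after anesthesia and before lumpectomy, is excluded. Rescue-dye subjects leave the efficacy cohort, which shows that the sponsor means to discount LUM data after dye. This stands and narrows the gap. It does not close it: the general permission for later dye carries no cohort exclusion, and for rescue-dye subjects the text does not say whether the node comparison counts as part of the efficacy cohort.

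**The wording may already exclude dye.** The resected nodes in 5.4.7 can be read as the same tracer-located nodes just mentioned, and the imaging procedure in 5.4.6 can be read to include node imaging. Both readings are possible. The first does not help, because a node found by tracer can also contain dye. The second conflicts with 6.2.6, which draws the line at the cavity. At best the text is ambiguous, and the same added sentence would settle it.

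**Little depends on it.** Node imaging is optional, no node sensitivity, specificity or detection threshold is defined, and the SAP plans no node analysis. This stands in full and limits the importance of the point.

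**A stronger inference is tempting.** A reader might infer that dye-exposed nodes will read LUM-positive whatever their histology, so that apparent node specificity falls and apparent sensitivity rises. The documents do not support that. Spectral overlap alone does not show that an exposed node crosses the threshold, or that the net effect is added rather than lost signal.

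**Conclusion.** The gap is real and narrow. Sections 5.4.6, 5.4.7 and 6.2.6, read together, let nodes imaged after a permitted later dye injection enter the exploratory comparison with a signal confounded by dye, and no protocol or SAP rule clearly removes or flags them.

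The conclusion rests on the protocol's own statement of overlap and on 6.2.6 marking where the dye restriction ends. It also assumes that some surgeons will both use dye after cavity imaging and choose to image nodes; how often is not given.

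The consequence is limited to interpretation of this optional endpoint. Cavity sensitivity and specificity, residual cancer removal, the algorithm lock, the sample size and the safety analysis do not use node images. The change is worth making because it is cheap and because dye status may not be recoverable later, not because any main result is at risk.

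**What to change.** 1. Add a worksheet and case report form field for each node image: whether a mapping dye had been injected and, if so, the time of injection relative to the image.
2. Add to 5.4.7 a sentence such as: *Node images taken after injection of any mapping dye are labelled as post-dye, excluded from the main LUM-versus-pathology comparison, and reported separately as reference only.*
3. State in the same place that this applies to rescue-dye subjects as well as to dye given after cavity imaging, so that 5.4.6, 5.4.7 and 6.2.6 agree.

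The cost is a short addition to the text, one data field, and fewer node images in the main comparison. Exclusion is not the only defensible handling, but the recording in item 1 is needed for any handling. Mapping practice does not change.

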## 5.5 Schema

The schema for Phase C of the Feasibility Study is shown below in Figure 6.

**Figure 6:** Phase C study schema.

## 6 SUBJECT SELECTION

### 6.1 Eligibility criteria

Subjects must meet the following criteria on screening examination to be eligible to participate in the study:

- 6.1.1 Subjects must have histologically or cytologically confirmed primary invasive breast cancer, ductal carcinoma in situ (DCIS) or a combination of invasive breast cancer and DCIS. The protocol accepted methods for obtaining the histological samples are diagnostic core needle biopsies or fine needle biopsies.
- 6.1.2 Female, age of 18 years or older. Because no dosing or adverse event data are currently available on the use of LUM015 in subjects <18 years of age, children are excluded from this study.

LUMICELL CONFIDENTIAL

This document is confidential. Do not disclose or use except as authorized.

- 6.1.3 Subjects must be scheduled for a lumpectomy for a breast malignancy.
- 6.1.4 Subjects must be able and willing to follow study procedures and instructions.
- 6.1.5 Subjects must have received and signed an informed consent form.
- 6.1.6 Subjects must have no uncontrolled serious medical problems except for the diagnosis of cancer, as per the exclusion criteria listed below.
- 6.1.7 Subjects must have normal organ and marrow function within limits as defined below:
  - Leukocytes  $\geq$  3,000/mcL
  - Platelets  $\geq$  75,000/mcL
  - total bilirubin within normal institutional limits
  - AST (SGOT)/ALT (SGPT)  $\leq$  2.5 X institutional upper limit of normal
  - Creatinine  $\leq$  1.5 mg/dL or creatinine clearance  $\geq$  60 mL/min/1.73 m^2 for subjects with creatinine levels above institutional normal.

- 6.1.8 Subjects with ECOG performance status of 0 or 1.

**Note:** Subjects with a history of multiple drug allergies, atopic subjects, and subjects with atopic syndrome are eligible for the study but should be pre-medicated according to institutional standards prior to injection of the LUM015 imaging agent.

